### **1.5.3.2 Secondary efficacy endpoints**

All secondary efficacy endpoints will be analyzed for the Full Analysis Set.

#### **Average pain intensity**

The change from baseline in the average pain intensity, recorded on the tablet computer, will be analyzed with an MMRM, including the covariate baseline pain intensity score, and the factors geographic region, week, treatment, and treatment-by-week interaction as fixed effects, and subject as random effect. An unstructured covariance matrix will be used to model the covariance structure.

The analysis will be performed using the contrast, i.e., the mixed model Wald test, of 400 mg neridronic acid versus placebo at Week 26 of the treatment, week and treatment-by-week interaction term of the mixed effects model described above. Model-based parameter estimates, standard errors, 95% confidence intervals, and p-values will be tabulated. This analysis will be performed using the observed values without imputation of missing values.

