### **1.5.3.1 Primary endpoint**

See Section 1.2 for the definition of the primary endpoint.

For the primary objective of the trial, the primary estimand is the difference in means of the primary efficacy endpoint of 400 mg intravenous neridronic acid compared to placebo for all allocated and treated subjects. This treatment policy or *de facto* estimand measures the effect of neridronic acid regardless of adherence to treatment or protocol.

The primary estimand will be estimated by the analysis of the primary efficacy endpoint for the Full Analysis Set. The primary analysis will fit a mixed model for repeated measures (MMRM) to the change from baseline in the average pain intensity scores from Week 1 to Week 12 recorded once daily in the electronic diary, including the covariate baseline pain intensity score, and the factors geographic region, week, treatment, and treatment-by-week interaction as fixed effects, and an unstructured covariance matrix to model the covariance structure of the repeated measurements.

The primary efficacy analysis will be performed using the contrast, i.e., the mixed model Wald test, of neridronic acid 400 mg versus placebo at Week 12 of the treatment, week and treatment-by-week interaction term of the mixed effects model described above. Model-based parameter estimates, standard errors, 95% confidence intervals, and p-values will be tabulated. This analysis will be performed using only the observed values without imputation of missing values.

Additional sensitivity analyses will be performed to assess the robustness of primary analysis results. Sensitivity analyses will include the imputation of missing pain intensity scores using different pattern mixture models (PMMs).

A descriptive summary of the weekly averages and the changes from baseline will be generated by treatment group. Graphical displays will be used if appropriate.

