#### **Dynamic mechanical allodynia**

The change from baseline in the DMA will be analyzed using a similar model as for average pain intensity. Only subjects with allodynia at baseline, i.e., a DMA score greater than 0 on the 0 to 10 NRS, will be included in the analysis.

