#### **Edema**

The change from baseline in edema will be analyzed using a similar model as for average pain intensity. Only subjects with presence of the CRPS sign “asymmetric edema” at baseline will be included in the analysis.

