#### 1.5.3.4 Confirmatory testing strategy for secondary endpoints

A confirmatory testing procedure will be used for testing of the superiority of neridronic acid 400 mg versus placebo with respect to the primary and selected secondary efficacy endpoints (change from baseline to Week 26 in the average pain intensity, change from baseline to Week 12 in the pain intensity level of DMA, change from baseline to Week 12 in the PPT ratio, and change from baseline to Week 12 in the ratio of figure of eight measurements).

First, the primary endpoint will be tested at a one-sided level  $\alpha = 2.5\%$ . If the first test is statistically significant, the 4 secondary endpoints will be tested in a second stage.

To control for the family-wise type I error rate at the one-sided 2.5% level, a hybrid Hochberg-Hommel step-up procedure (hybrid-0 procedure in Gou et al. 2014) will be applied. The testing procedure uses the ordered p-values  $p_{(1)} \geq p_{(2)} \geq p_{(3)} \geq p_{(4)}$ . At first, if the largest p-value  $p_{(1)} \leq \alpha$ , then all 4 hypotheses are rejected. Otherwise the associated null hypothesis  $H_{(1)}$  is accepted and testing proceeds to the next step. In general, at Step  $i = 2,..,4$ , if  $p_{(i)} \leq c_i\alpha$ , then any hypothesis with p-value  $\leq d_i\alpha$  will be rejected and testing stops; otherwise the null hypothesis  $H_{(i)}$  and testing continues at the next step. At Step 4, the null hypothesis  $H_{(4)}$  is rejected if  $p_{(4)} \leq \alpha/4$ ; otherwise  $H_{(4)}$  is accepted. The constants used in the testing procedure are defined by  $c_i = (i+1)/(2i)$  and  $d_i = 1/i$  and are given in the table below.

i	1	2	3	4
$c_i$	1	3/4	2/3	5/8
$d_i$	1	1/2	1/3	1/4

This semiparametric multiple testing procedure controls the family-wise error rate in the strong sense if the test statistics follow a multivariate normal distribution with non-negative correlation coefficients (Gou et al. 2014) which can be assumed for the investigated 4 efficacy endpoints.

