### **7 TRIAL OBJECTIVES AND ENDPOINTS**

The trial objectives and endpoints are given in Section [1.2](#).

The pain intensity score used for the primary endpoint will be calculated from average pain intensity ratings, assessed once daily in the electronic diary and referring to the CRPS-affected limb. The baseline average pain intensity score is defined as the average of the week before allocation to treatment at Visit 2 and calculated as the average of the 7 average pain intensity ratings starting in the evening of Day -7 until Day -1. A baseline pain intensity score ( $\geq 4$  on the NRS) must be confirmed at the site prior to subject allocation (at Visit 2). Subjects who do not meet eligibility criteria due to inadequate pain ( $< 4$  on the NRS) will be excluded from the trial.

Pain intensity scores from Week 1 through Week 12 will be calculated in a similar manner using average pain intensity ratings obtained from the electronic diary. The Week 12 pain intensity score, for evaluation of the primary outcome, will be the average of up to 7 possible ratings obtained in the 7-day period culminating with the rating obtained in the evening prior to the Week 12 visit.

Handling of missing pain ratings will be addressed in the statistical analysis plan. Compliance with the pain ratings in the electronic diary must be monitored and subjects with insufficient ratings ( $< 4$  ratings per week for 2 weeks) should receive a reminder and undergo re-training.

During Visit 2 (Day 1), Visit 7 (Week 6), Visit 8 (Week 12), Visit 9 (Week 16), and Visit 11 (Week 26), Visit 16 (Week 36), and Visit 17 (Week 52), the subjects will be asked to record the pain intensity ratings for average, worst, and current CRPS-related pain directly on a tablet computer maintained at the site. For subjects included in Treatment Period B, the subjects will also be asked to record pain intensity rating at Visit 12, Visit 13, Visit 14, and Visit 15. Worst and average pain intensity ratings will be based on a 24-hour recall period. The pain ratings and other patient-reported outcomes from the tablet computers recorded up to Week 26 as well as DMA, edema, and PPT assessment will be used for the secondary endpoints.

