#### **Average pain intensity**

The change from baseline in the average pain intensity, recorded on the tablet computer, will be analyzed with an MMRM, including the covariate baseline pain intensity score, and the factors geographic region, week, treatment, and treatment-by-week interaction as fixed effects, and subject as random effect. An unstructured covariance matrix will be used to model the covariance structure.

The analysis will be performed using the contrast, i.e., the mixed model Wald test, of 400 mg neridronic acid versus placebo at Week 26 of the treatment, week and treatment-by-week interaction term of the mixed effects model described above. Model-based parameter estimates, standard errors, 95% confidence intervals, and p-values will be tabulated. This analysis will be performed using the observed values without imputation of missing values.

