Formerly read:	Now reads:
from baseline in the average pain intensity scores from Week 1 to Week 12 recorded once daily in the electronic diary, including the covariate baseline pain intensity score, and the factors geographic region, week, treatment, and treatment-by-week interaction as fixed effects, and <del>subject as random effect</del> . An unstructured covariance matrix <del>will be used</del> to model the covariance structure.	from baseline in the average pain intensity scores from Week 1 to Week 12 recorded once daily in the electronic diary, including the covariate baseline pain intensity score, and the factors geographic region, week, treatment, and treatment-by-week interaction as fixed effects, and an unstructured covariance matrix to model the covariance structure of the repeated measurements .
Section 1.5.3.2: Secondary efficacy endpoints Section 14.1.7.2: Analysis of the secondary efficacy endpoints	
Pain response to treatment [...] A logistic regression model will be fitted to the data, including the covariate baseline pain intensity score, and the factors geographic region, <del>week</del> , treatment, <del>and treatment-by-week interaction</del> as fixed effects. Model-based parameter estimates, standard errors, 95% confidence intervals, and p-values for the odds ratio at Week 12 and Week 26 between 400 mg neridronic acid and placebo will be tabulated.	Pain response to treatment [...] A logistic regression model at Week 12 and Week 26 will be fitted to the data, including the covariate baseline pain intensity score, and the factors geographic region, and treatment as fixed effects. Model-based parameter estimates, standard errors, 95% confidence intervals, and p-values for the odds ratio at Week 12 and Week 26 between 400 mg neridronic acid and placebo will be tabulated.
Section 1.6.1: Visit 1 to Visit 10	

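### Does naming both a random subject effect and an unstructured covariance matrix leave the Week 26 pain model, and the three endpoints that borrow it, undetermined?

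*Protocol*

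**What the plan says.** Protocol Section 1.5.3.2 (Average pain intensity), repeated in Section 14.1.7.2, analyses tablet-recorded pain with an MMRM. The covariates and factors are baseline pain, region, week, treatment and their interaction, described as "treatment-by-week interaction as fixed effects, and subject as random effect. An unstructured covariance matrix will be used to model the covariance structure". The test is a Wald contrast at Week 26 with model-based standard errors.

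The primary diary-pain model in Sections 1.5.3.1 and 14.1.7.1.1 has the same fixed effects, no random subject effect, and "an unstructured covariance matrix to model the covariance structure of the repeated measurements".

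DMA and the PPT ratio each "will be analyzed using a similar model as for average pain intensity". For the third, "The change from baseline in edema will be analyzed using a similar model as for average pain intensity". Section 1.5.3.4 makes these three, with Week 26 pain, the confirmatory secondary family: "If the first test is statistically significant, the 4 secondary endpoints will be tested in a second stage". Section 14.1.2 leaves full analysis details to the statistical analysis plan.

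**The concern.** An MMRM with an unstructured within-subject matrix needs no random subject effect, because the matrix already carries all between-visit covariance. Naming both invites the question of what the matrix describes. There are three possible answers:

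1. Subject is named loosely as the clustering unit, and the matrix covers the repeated measurements.
2. A random intercept is added on top of an unstructured residual matrix.
3. The matrix belongs to the random effect only, with independent residuals.

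The second is over-parameterised and may produce a singular Hessian, failed convergence, or a fallback chosen at the time of fitting. The third is compound symmetry, whose standard error at Week 26 pools variance over visits and is wrong when the variance changes over time. Three other endpoints take a similar model, so every second-stage confirmatory test would be touched. The protocol's own primary model shows clearer wording, which makes the difference look like an oversight with consequences.

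**Working it through.** **Inputs.** Planned size is 180 subjects, 90 per arm, and the primary-endpoint SD is 2.0 (Section 1.5.1). The level is one-sided 2.5% (Section 1.5.3.4). Tablet pain is recorded after baseline at Weeks 6, 12, 16, 22 and 26 (Sections 1.6.1 and 1.6.2), so T = 5. The list in Section 7, "Visit 8 (Week 12), Visit 9 (Week 16), and Visit 11 (Week 26", skips Week 22 and would give T = 4. DMA, PPT and edema are measured at Weeks 6, 12 and 26, so T = 3. The protocol gives no SD by visit, so any SD trend below is an assumption.

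**The plan's own figure.** For a difference of 1.0, SD 2.0, one-sided 2.5% and 90% power, the noncentral t gives 89.99% at 85 per arm and 90.3% at 86, so the stated 86 is reproduced. It concerns the primary endpoint and does not use the covariance model in question.

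**Reading 1.** The model is the primary model applied to tablet pain. Nothing changes.

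**Reading 2.** The marginal covariance is V = τ²J + R, with R unstructured and J a matrix of ones. Replacing (τ², R) by (τ² + δ, R − δJ) leaves V unchanged, so one parameter is redundant:

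| Visits T | Parameters T(T+1)/2 + 1 | Rank |
|---|---|---|
| 5 | 16 | 15 |
| 4 | 11 | 10 |
| 3 | 7 | 6 |

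The treatment contrast and its standard error depend on the data and on V only. Every V available with R alone is reached at τ² = 0, so the maximised likelihood is the same. A simulated REML fit confirms this (assumed: 180 subjects, SD 2.0, five visits, about 15% dropout). With and without the random intercept, the negative restricted log-likelihood was 862.5182, the Week 26 difference -0.5954 and the standard error 0.32779. What changed was the smallest Hessian eigenvalue, from 16.9 to zero within 0.0001. The τ² estimate stayed near its start value (0.050, 0.485 and 0.952 from starts of 0.05, 0.5 and 1.0). The unidentified quantity is a nuisance parameter that nobody will report.

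**Reading 3.** With complete data, compound symmetry uses the pooled SD, so the one-sided error at the tested visit is 1 − Φ(1.96 × pooled SD / SD at that visit). For SDs of 1.6, 1.8, 2.0, 2.2 and 2.4, the pooled SD is √(20.40/5) = 2.020. The ratio at Week 26 is 2.020/2.4 = 0.842, and 1 − Φ(1.650) = 5.0%. All trends tried:

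| Assumed SD range over five visits | Rising | Falling |
|---|---|---|
| constant 2.0 | 2.5% | 2.5% |
| 1.8 to 2.2 | 3.7% | 1.5% |
| 1.6 to 2.4 | 5.0% | 0.7% |
| 1.4 to 2.6 | 6.2% | 0.2% |

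A simulation of 1,500 trials per scenario (assumed dropout of about 3.5% per interval and serial correlation of 0.97 per week) gave 5.1% under compound symmetry against 2.7% unstructured for SD rising 1.6 to 2.4. For the falling trend it gave 1.1% against 2.4%.

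For DMA, PPT and edema, Week 12 is the middle of three visits. With SDs (1.8, 2.0, 2.2), (1.6, 2.0, 2.4) and (1.4, 2.0, 2.6) the error is 2.46%, 2.35% and 2.18%. The distortion therefore essentially vanishes for three of the four tests.

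The Week 26 rates are also for a single test at the full 2.5%. Section 1.5.3.4 requires the primary test to succeed first. It then applies the full level to Week 26 only if all four p-values are at or below 2.5%. Otherwise the threshold is α/2, α/3 or α/4, that is 1.25%, 0.83% or 0.625%. The tabulated rates are upper bounds on a false Week 26 claim under reading 3.

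**Which reading does the text support?** The section calls the analysis an MMRM and says an unstructured matrix models the covariance structure. With subject as one random intercept, a matrix attached to that effect is 1 × 1. Unstructured then says nothing, and the fitted model is compound symmetric, which contradicts the sentence. Reading 3 is not a natural one. Readings 1 and 2 give the same inference.

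**The case for a change.** The best case for a change is that the protocol is not silent here. It states a covariance model in two sections, and the statistical analysis plan can only repeat that wording or depart from it. A confirmatory test should admit one analysis, and literal text that is either over-parameterised or not unstructured falls short of that. Amendment 01 (Section 19.1) replaced the same phrase in the primary-analysis sections with an "unstructured covariance matrix to model the covariance structure of the repeated measurements" and left the secondary sections alone. The repair would cost a few words.

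Part of this stands. The mismatch between the two models is real, and a random intercept taken literally is redundant. If the text is reopened for another reason, aligning it would be tidy.

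The rest does not carry. More than one wording does not mean more than one result, since the two natural readings agree in estimate and standard error. The amendment log records superseded text and cannot show an error. If anything it supports reading 1: the replacement is not among the principal changes listed in the amendment rationale, which fits a clarification rather than a new model. Convergence warnings and fallbacks are implementation details that Section 14.1.2 refers to the statistical analysis plan, which is not at hand. The three borrowing endpoints are said to use a similar model, so exact inheritance of the phrase is an inference.

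**Conclusion.** No change is needed. The phrase "subject as random effect. An unstructured covariance matrix will be used to model the covariance structure" is loose, and an analyst who meets it will fit the unstructured model that the primary section spells out. If the redundant intercept is added and the fit converges, the contrast and its standard error are the same. The primary analysis and the sample size are untouched.

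The only route to a different p-value is the compound-symmetry reading, with a one-sided error between 0.2% and 6.2% at Week 26. Those figures rest on assumed SD trends that the protocol does not give, and on a reading that makes its key word meaningless. For the Week 12 endpoints the error stays at 2.2% to 2.5% even then. Harmonising the wording would be an editorial improvement with no gain in the validity of any planned test.

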#### **Pain response to treatment**

Pain response to treatment, defined as an at least 30% decrease from baseline in average pain intensity, recorded on the tablet computer, will be derived. If a subject shows a worsening or the pain intensity score for the respective visit is missing then the subject will be considered a pain non-responder for the respective visit. A logistic regression model at Week 12 and Week 26 will be fitted to the data, including the covariate baseline pain intensity score, and the factors geographic region, and treatment as fixed effects. Model-based parameter estimates, standard errors, 95% confidence intervals, and p-values for the odds ratio at Week 12 and Week 26 between 400 mg neridronic acid and placebo will be tabulated.

The analysis of pain response to treatment will include a cumulative responder analysis at Week 12, Week 26, and Week 52, where responder rates will be calculated for different percentage thresholds for decrease from baseline in average pain intensity.

#### **Dynamic mechanical allodynia**

The change from baseline in the DMA will be analyzed using a similar model as for average pain intensity. Only subjects with allodynia at baseline, i.e., a DMA score greater than 0 on the 0 to 10 NRS, will be included in the analysis.

#### **Pressure pain threshold**

The change from baseline in the ratio of the PPT in the affected limb to the PPT in the unaffected limb for the thenar muscle/abductor hallucis muscle will be analyzed using a similar model as for average pain intensity. Only subjects with deep somatic pain ( $PPT \leq 300$  kPa) in the affected limb at baseline will be included in the analysis.

#### **Edema**

The change from baseline in edema will be analyzed using a similar model as for average pain intensity. Only subjects with presence of the CRPS sign “asymmetric edema” at baseline will be included in the analysis.

### 1.5.3.3 Missing data handling

Diligent attempts will be made to limit the amount of missing data in the primary efficacy endpoint. Efforts will be made to follow-up subjects who discontinue treatment and to collect the primary efficacy endpoint for the statistical analysis.

The primary analysis using the MMRM is based on the missing-at-random (MAR) assumption. For the treatment policy or de facto estimand, the MAR assumption is justified for neridronic acid owing to the long half-life in bone and the anticipated persistent effect over the 12-week trial period. It can be assumed that the effect of neridronic acid continues after the treatment period is completed, and it also persists after the treatment period regardless of trial completion or early discontinuation. Therefore, the response of discontinued subjects will not change if the subjects continue to receive the stable therapy that they receive during the 12-week trial period up to Visit 8. If subjects change their treatment after discontinuation from the trial, it is nevertheless reasonable to assume that their response is not significantly altered as there are currently no established effective treatments. Hence, the MAR assumption is considered a plausible missingness mechanism for the primary estimand in the case of neridronic acid.

The MAR assumption cannot be verified based on data observed in the trial. Deviations from MAR cannot be excluded and several plausible missing-not-at-random (MNAR) assumptions will be investigated to assess their impact. MNAR assumptions will be defined via PMMs specifying the distribution of missing values, e.g., for subjects discontinuing before the end of the trial. Plausible PMMs for the primary estimand are placebo multiple imputation (PMI) and the delta shift method.

Placebo multiple imputation is a reference-based approach based on the copy reference method. It models the means of missing values in the active arm based on the means observed in the placebo arm (reference arm). The method assumes that the response of discontinued subjects in the active arm gradually approaches the response in the placebo arm and eventually no effect of neridronic acid persists after a subject discontinues. For neridronic acid this appears conservative in light of the anticipated persistent effect.

The delta shift method models the means of missing values in the active arm by adding a pre-specified value  $\Delta$  to the observed means in the active arm. The method includes a tipping point analysis, which is defined as the delta that must be added in order to overturn conclusions from the primary analysis from statistically significant to statistically insignificant. The method assumes that discontinued subjects in the active arm have higher pain compared to subjects who stay in the trial. Again this seems conservative if persistence of effect can be assumed for neridronic acid.

Overall, the 2 PMMs can be considered more conservative than MAR because they model missing pain intensity scores in the active arm using higher mean values than the means actually observed, whereas the placebo arm is not changed. In this way, neridronic acid is effectively penalized under these assumptions.

In summary, for neridronic acid the MAR assumption seems to be the most plausible missingness assumption for analyses estimating the primary estimand. It will be supplemented by sensitivity analyses based on MNAR assumptions representing plausible and reasonably conservative deviations from MAR.

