### 1.5.1 Sample size rationale

The sample size is based on a statistical test of the superiority of 400 mg neridronic acid versus placebo in the primary endpoint. The null hypothesis of no effect,  $H_0: 0 \leq \mu_{400} - \mu_0$ , is tested against the alternative hypothesis  $H_1: \mu_{400} - \mu_0 < 0$ . (Note: A pain reduction will be analyzed as a negative change from baseline. An effective treatment will lead to reduced pain and, hence, to a negative mean change from baseline,  $\mu < 0$ ).

For a difference in the means of  $\mu_{400} - \mu_0 = -1.0$  points on the NRS, assuming a standard deviation of 2.0 points on the NRS and a 1-sided significance level of 2.5% ( $\alpha = 0.025$ ), 86 subjects per arm will be required to provide at least 90% power ( $1-\beta = 0.9$ ) to reject the null hypothesis. To compensate for a slight decrease in power due to an optional futility interim analysis, a total of 180 subjects (90 subjects per arm) are planned to be allocated to treatment.

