# **6 INTRODUCTION AND TRIAL BACKGROUND**

## **6.1 Introduction**

Complex regional pain syndrome is a severe and frequently chronic disabling condition that can develop after a minor injury, such as a fracture or sprain, usually in a distal extremity (hand, wrist, ankle, and foot). Complex regional pain syndrome is characterized by disproportionate pain, relative to the inciting event, and signs and symptoms related to sensory, vasomotor and sudomotor abnormalities, trophic changes (abnormal skin, hair, and nails), and impaired motor function in the affected limb (Harden et al. 2010a). There are currently no Food and Drug Administration (FDA) approved pharmacological treatments for CRPS, and patients are underserved due to a poor understanding of the pathophysiological processes and lack of evidence for effective treatments (Harden et al. 2013; Goebel 2013; Bruehl 2015).

Randomized placebo-controlled trials of bisphosphonates in patients with CRPS suggest that these agents are efficacious for treatment of pain and other symptoms associated with this syndrome (Brunner et al. 2009; Cossins et al. 2013; O'Connell et al. 2013; Varenna et al. 2013; Wertli et al.

2014). Since bisphosphonates act to suppress osteoclastic bone resorption, it is likely that bone pathology plays a role in the evolution and maintenance of CRPS Type I (CRPS-I; Gatti et al. 2016), although other mechanisms may be involved (Varennna et al. 2013). Evidence of osteopenia and increased uptake of radiolabeled bisphosphonate tracer (observed during bone scintigraphy) in the affected limb(s) of patients with CRPS provides support for this hypothesis. Therefore, the present trial with a total dose of neridronic acid 400 mg is designed to obtain efficacy and safety information to support the potential broader use of neridronic acid to address a major unmet medical need in patients with CRPS.

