### **8.1.2 Rationale for the investigational medicinal products and the selected doses**

A previous pilot trial of neridronic acid, including cumulative intravenous doses of 200 mg, 300 mg, and 400 mg, suggested that doses below 400 mg were suboptimally effective (Varennna et al. 2004).

A previous randomized, double-blind, placebo-controlled trial performed by Abiogen Pharma S.p.A. demonstrated that a 400 mg cumulative intravenous dose of neridronic acid is effective, safe, and well tolerated in subjects with CRPS-I (Varennna et al. 2013; Clinical Study Report

NERI-AS001-07). As the 4 x 100 mg dose regimen used in that trial has been approved for treatment of CRPS-I in Italy, the same dose regimen was selected for investigation in this trial.

In Italy, the recommended infusion time for 100 mg neridronic acid to treat osteogenesis imperfecta and CRPS-I is 2 hours. To limit the maximum concentrations ( $C_{max}$ ) in this trial to levels similar to (and unlikely to exceed) those obtained in the KF7013-01 trial, in which 62.5 mg neridronic acid was infused in 2 hours, the infusion time has been extended to 4 hours.

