## **10.3        Method of assigning subjects to treatment (allocation)**

On Day 1, subjects who comply with all inclusion criteria and do not meet any of the exclusion criteria will be randomly allocated to 1 of the 2 treatment groups in a 1:1 ratio stratified by geographic region. Treatment assignment will be performed centrally using an interactive response technology system prior to the first intravenous infusion of IMP. The details of the vendor and system will be filed in the trial master file.

The investigator (or delegate) must log into the system using their own user identification number and a password. The investigator (or delegate) will enter the subject's number and other information required by the system to obtain a medication number. The medication number will then be used to select the correct package of IMP to give to the subject.

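### The two named MNAR sensitivity analyses shift only the active arm, so the tipping point can overstate robustness if more placebo values are missing

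*Protocol*

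**What the plan says.** Protocol Section 1.5.3.1 defines a treatment-policy estimand at Week 12 that applies whether or not subjects adhere to treatment or protocol. The primary MMRM uses observed values under MAR.

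Section 1.5.3.3, repeated in 14.1.7.3, names two MNAR models. Placebo multiple imputation draws missing active values towards the placebo means. The delta shift adds a value to missing active values and includes the tipping point. The protocol ranks both as stricter than MAR because they model missing active values "using higher mean values than the means actually observed, whereas the placebo arm is not changed".

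The same section foresees that subjects may change treatment after leaving, and answers that "it is nevertheless reasonable to assume that their response is not significantly altered as there are currently no established effective treatments".

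Other sections read differently. Section 6.1 says that placebo-controlled trials of bisphosphonates "suggest that these agents are efficacious for treatment of pain and other symptoms associated with this syndrome". Section 8.1.2 explains the choice of regimen thus: "As the 4 x 100 mg dose regimen used in that trial has been approved for treatment of CRPS-I in Italy".

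**The concern.** MAR predicts a missing placebo value from placebo subjects who remain in the trial. Those subjects are meant to stay on stable therapy. Section 1.4.2.1 bars them from bisphosphonates, nerve blocks, ketamine infusions and systemic steroids, and Section 8.1.1 prohibits new therapies. A subject who leaves returns to ordinary care (Section 11.5) and is no longer bound by these rules. The diary that carries the primary endpoint is handed back at early termination (Section 1.6.1, footnote q), so such a subject will normally supply no Week 12 value.

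The main argument for MAR is that neridronic acid persists in bone. That says nothing about subjects who received placebo. For them, MAR after a change of therapy rests on the single sentence about the lack of established treatments.

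At stake is the robustness statement, not the primary test or its type I error. An active-only tipping point can look comfortable simply because few active values are missing, while a smaller shift among more numerous missing placebo values would change the conclusion.

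**Working it through.** **Inputs from the protocol.** Section 1.5.1: difference -1.0, SD 2.0, one-sided 2.5%, "86 subjects per arm will be required to provide at least 90% power", and "a total of 180 subjects (90 subjects per arm) are planned to be allocated to treatment". Section 10.3: "1 of the 2 treatment groups in a 1:1 ratio stratified by geographic region".

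**Assumed inputs.** The protocol gives no dropout rate, so missing shares at Week 12 are varied. The observed effect is also assumed: -0.80, and -1.0 for comparison.

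**Plan's own figure.** The normal approximation gives 85 per arm. With the t-test, power is 0.8999 at 85 and 0.9032 at 86, so 86 is reproduced. At 90 per arm it is 0.916.

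**Margin.** SE = 2.0 × √(2/90) = 0.298. The t critical value on 178 degrees of freedom puts the significance threshold at 0.588. An observed -0.80 leaves 0.80 - 0.588 = 0.212 points to lose. (With 1.96 × 0.298 = 0.584 the margin is 0.216, and the results below barely move.)

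**Tipping condition.** Let pA and pP be the missing shares, dA the worsening added to missing active values, and dP the improvement given to missing placebo values. Significance is lost when

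pA × dA + pP × dP = margin.

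The protocol's tipping point fixes dP = 0.

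| Observed effect | Missing active / placebo | Active-only tip | Placebo-only tip |
|---|---|---|---|
| -0.80 | 10% / 30% | 0.212/0.10 = 2.12 | 0.212/0.30 = 0.71 |
| -0.80 | 10% / 20% | 2.12 | 1.06 |
| -0.80 | 5% / 20% | 4.23 | 1.06 |
| -0.80 | 5% / 5% | 4.23 | 4.23 |
| -1.0 | 10% / 30% | 4.12 | 1.37 |
| -1.0 | 5% / 5% | 8.23 | 8.23 |

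**Combined shifts.** Take -0.80 with 10% / 30% missing. A placebo gain of 0.5 uses 0.30 × 0.5 = 0.15 of the margin, so the active tip falls from 2.12 to (0.212 - 0.15)/0.10 = 0.62. A placebo gain of 1.0 moves the estimate to -0.80 + 0.30 = -0.50, one-sided p = 0.048, which is not significant at 0.025.

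The SE is held fixed throughout. Added imputation variance would lower every tipping value.

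**The case against.** The case for the plan has real substance.

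- **The assumption has support.** The choice-of-control text in Section 8.1 cites a systematic review that found only poor-quality evidence for any CRPS intervention. Inclusion criterion 5 requires two failed treatments. Section 6.3 reports that lower doses of this drug did not separate from placebo. This makes a large placebo gain less likely but does not test for one.
- **Some changes of therapy will be observed.** Starting a barred therapy is not a compulsory reason for leaving the trial (Section 9.3.1, Table 1), and subjects who withdraw are asked to continue follow-up if possible (Section 8.2). Such data would inform the MAR prediction. This narrows the gap without closing it.
- **The direction could be the reverse.** A placebo subject who leaves for lack of effect may have more pain than MAR predicts. Leaving placebo at MAR would then work against the drug.

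Three stronger readings are tempting, and the protocol does not support them. A reader might infer that a placebo-arm departure will never be tested. The protocol says only that the sensitivity analyses will include such models, and the SAP, which was not available here, could add others. A reader might infer that the claim of conservatism is false. As a comparison with MAR it is correct, because both models penalise the active arm; it simply does not bound a placebo gain. A reader might also infer that a plainly modest placebo shift overturns the result. At 5% / 20% missing and -0.80, the placebo tip of 1.06 exceeds the 1.0-point effect assumed for the full drug course. A 1.0-point gain in every missing placebo subject would use 0.20 of the 0.212 margin, leaving -0.60 with one-sided p = 0.023.

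**Conclusion.** The point stands as a limitation of the two models the protocol names. They leave the placebo arm at MAR under an estimand that counts pain after a change of therapy, on an untested assumption that sits uneasily with Sections 6.1, 6.2 and 8.1.2.

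The size is conditional on assumed dropout and on the assumed observed effect. It is material when placebo loses clearly more subjects than active and the observed effect lies near the threshold. At 10% / 30% and -0.80, the planned analysis would report about 2.1 points while a placebo shift of about 0.7 suffices. That 0.71 would arise if about 71% of the missing placebo subjects each gained 1.0 point. With equal missing shares the single-arm tips coincide, and at about 5% in each arm the matter is minor. It is a cheap improvement worth making, not a flaw in the primary analysis.

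**What to change.** In Sections 1.5.3.3 and 14.1.7.3, define the tipping-point analysis on a two-way grid. Add a delta of 0 or more to missing active values and a delta of 0 or less to missing placebo values, vary the two independently, and report the region in which significance is lost. Keep the sentence ranking the two models as stricter than MAR, but limit it to departures from MAR in the active arm.

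The cost is protocol and SAP wording and a few extra runs of the same imputation code, with no new data. The downside for the sponsor is that the robustness statement may turn out less favourable.
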